7.0 VISIT SCHEDULE AND ASSESSMENTS

7.1 Study Procedures

The visit schedule and assessments are summarized in [Table 1-1](#).

7.2 Study Visits and Assessments

7.2.1 Visit 1 – Screening (Visit 1, Day –30 to Day 1)

Screening procedures should be completed no more than 30 days prior to the baseline visit (Day 1), except when required to meet the contraception and pregnancy test requirements for women of childbearing potential. The following screening procedures are to be performed:

- Review study information with the subject or with his/her legal guardian and obtain written informed consent, including photographic consent.
- Count the acne nodules on the subject's face.
- Review inclusion and exclusion criteria with the subject to determine the subject's eligibility.
- Collect medical history and demographic information.
- Review and record prior medication (used within the previous 30 days) and concomitant medication (medications currently used).
- Perform a physical examination, including height and weight.
- Measure vital signs (systolic and diastolic blood pressure, heart rate, and respiratory rate) with subject in a seated position.
- For females of childbearing potential, obtain the date of the subject's last menstrual period and information on her contraceptive use.
- Perform a serum pregnancy test in all female subjects of childbearing potential (a urine pregnancy test may also be performed if the site holds the appropriate certifications). Counsel all female subjects on the use of at least 2 approved form(s) of contraception and provide pregnancy prevention information. Register for the iPLEDGE program. Female subjects of childbearing potential must comply with the mandatory contraception and pregnancy testing requirements of the iPLEDGE program (see also [Section 6.6](#) and [Section 7.4.5](#)).
- Obtain blood samples for a laboratory profile including hematology, fasting clinical chemistry, and a fasting lipid profile.

- If subject meets the inclusion/exclusion criteria, schedule Visit 2. Instruct the subject on fasting prior to the visit.

7.2.2 Active Treatment Period – Visit 2 – Baseline (Day 1)

Reminder: Before receiving study medication, female subjects of childbearing potential must have completed a 30-day waiting period during which they use two effective forms of contraception; had a negative screening pregnancy test at the end of the 30-day period, and then a second, confirmatory negative pregnancy test conducted at least 19 days after the first pregnancy and during the first 5 days of the menstrual period. If subjects do not have regular menstrual periods, eg, due to contraception choice, then they must still have two negative pregnancy tests.

- Review inclusion and exclusion criteria to ensure that the subject is qualified for study participation.
- Review and record medication used since Screening and update medical history.
- Obtain blood samples for a laboratory profile including fasting clinical chemistry and a fasting lipid profile.
- For females of childbearing potential, obtain the date of the subject's last menstrual period and information on her contraceptive use.
- Perform a UPT for females of childbearing potential. Ensure that female subjects of childbearing potential meet the iPLEDGE requirements.
- Take baseline photographs of the subject's face (see [Section 7.2.13](#)).
- Have the subject complete the acne-QOL questionnaire.
- Complete the baseline lesion count and IGA.
- Record any AEs.
- Prescribe the 30-day supply of study medication.
- Schedule the next study visit. Remind subject not to eat prior to the visit and to bring any unused capsules and used packaging with them to the visit.

7.2.3 Active Treatment Period – Visit 3 (Week 2 ± 4 days)

- Reconcile the medication use and record the number of missed doses as indicated in the diary
- Review any concomitant medication used since the previous study visit.
- Review laboratory test results from the Visit 2 assessment.
- Query the subject regarding consumption of food around the time of dosing.

- Obtain blood samples for a laboratory profile including fasting clinical chemistry, and a fasting lipid profile.
- Perform a serum pregnancy test for females of childbearing potential. Ensure that female subjects of childbearing potential are following the iPLEDGE requirements.
- Record any AEs.
- Schedule the next study visit. Remind subject not to eat prior to the visit and to bring any unused capsules and used capsule packaging with them to the visit.

7.2.4 Active Treatment Period – Visits 4, 5, 6, and 7 (Weeks 4, 8, 12, and 16 ± 4 days)

- Reconcile the medication use and record the number of missed doses per the diary.
- Review any concomitant medication used since the previous study visit.
- Query the subject regarding consumption of food around the time of dosing and remind subject that dosing should be at least one hour before a meal or at least two hours after a meal.
- Obtain blood samples for a laboratory profile including fasting clinical chemistry and a fasting lipid profile.
- Perform a serum pregnancy test for females of childbearing potential. Ensure that female subjects of childbearing potential are using 2 approved method(s) of contraception.
- Have the subject complete the acne-QOL questionnaire.
- Complete the lesion count and IGA.
- Record any AEs.
- Obtain photographs of the subject's face.
- Prescribe a 30-day supply of study medication.
- Schedule the next study visit. Remind subject not to eat prior to the visit and to bring any unused capsules and used capsule packaging with them to the visit.

7.2.5 Active Treatment Period – Visit 8/End of Treatment Visit (Week 20 ± 4 days)

- Reconcile the medication use and record the number of missed doses per the diary.
- Review any concomitant medication used since the previous study visit.
- Query the subject regarding consumption of food around the time of dosing.
- Measure vital signs (systolic and diastolic blood pressure, heart rate, and respiratory rate) with subject in a seated position and record weight.
- Obtain blood samples for a laboratory profile including fasting clinical chemistry, and a fasting lipid profile.
- Perform a serum pregnancy test for females of childbearing potential. Ensure that female subjects of childbearing potential are using 2 approved method(s) of contraception.

- Take EOT photographs of the subject's face (see [Section 7.2.13](#)).
- Have the subject complete the acne-QOL questionnaire.
- Complete the lesion count and IGA.
- Record any AEs.
- Schedule the next study visit.

7.2.6 Post Treatment Period – Visit 9 (Week 24 ± 4 days 4 weeks post treatment safety visit)

- Review any concomitant medications that affect acne (including all antibiotics) used since the previous study visit.
- Measure vital signs (systolic and diastolic blood pressure, heart rate, and respiratory rate) with subject in a seated position and record weight.
- Obtain blood samples for a laboratory profile including fasting clinical chemistry and a fasting lipid profile.
- Perform a serum pregnancy test for females of childbearing potential and counsel on any continued birth control needs (iPLEDGE does not require birth control to continue for more than 30 days post last dose)
- Record any AEs.
- Schedule the next study visit.

7.2.7 Post Treatment Period – Visits 10 to 14 (Weeks 32, 46, 72, 98, and 124 ± 2 Weeks)

- Review any concomitant medications that affect acne (including all antibiotics) used since the previous study visit.
- Take photographs as specified for the site (see [Section 7.2.13](#)).
- Have the subject complete the acne-QOL questionnaire.
- Complete the lesion count and IGA.
- Record any SAEs related to study medication.
- At Visits 10, 11, 12, and 13, schedule the next study visit.
- If an acne flare occurs during the PTP, the subject is to notify the site and report for an unscheduled visit at which acne severity will be assessed and treatment options will be considered. If the subject refuses to return, the investigator is to attempt to determine the acne severity and type of retreatment through discussion with the subject and with the subject's prescribing physician.

7.2.8 Early Termination

If a subject withdraws from the study during the ATP and prior to Week 20/Visit 8, the subject is to return to the site. All EOT procedures should be performed, including the administration of

the acne-QOL questionnaire, the lesion count, the IGA, and a pregnancy test (if applicable). The photography should be performed using the method assigned to the site.

If a subject withdraws from the study during the PTP and prior to Visit 14, the subject is to return to the site for an early termination visit. All EOS procedures should be performed, including the acne QOL, lesion count, the IGA, and photography. Subjects who require an additional course of isotretinoin therapy are to be discontinued after the EOS procedures are performed.

7.2.10 Quality of Life Assessment

Beginning at Baseline, subjects will be asked to complete an acne-QOL at each visit, except Visit 3 and 9.

7.2.11 Lesion Count

Lesion counts will be performed at every visit, except Visits 3 and 9. Qualified trained medical practitioners will make counts of nodules and inflammatory lesions (papules and pustules) on the face and record the counts separately. Where possible, the same individual will perform all lesion counts for a subject.

7.2.12 Investigator's Global Assessment (IGA)

The IGA is a static assessment that is independent of the baseline score. A qualified trained medical practitioner will perform the IGA at every visit beginning at Visit 2, except Visits 3 and 9. The evaluator should make the assessments without referring to the baseline value. It is preferred that the same evaluator performs all assessments for a subject to the extent possible. The grading system for the IGA is shown in [Table 7-1](#).

Table 7-1 Investigator's Global Assessment

Grade	Description	Acne Disease Status
0	Clear	No papules/ pustules present; no nodules present; no comedones present; residual hyperpigmentation and/or erythema may be present; acne scars may be present.
1	Almost clear	A few scattered small papules/pustules may be present; no nodules present; a few scattered comedones may be present.
2	Mild	Some papules/pustules present; no nodules present; some comedones may be present.
3	Moderate	Many papules/pustules present; up to 2 nodules may be present; some or many comedones may be present.
4	Severe	Several papules/pustules and many nodules (>2) present, some to several comedones may be present.
5	Very severe	Highly inflammatory acne with several papules/pustules covering the face with several nodules present; some to several comedones may be present.

Source: [Tan et al¹⁶](#)

7.2.13 Photography

Subjects will consent to photography prior to enrollment in the study; consent for photography is mandatory for participation in the study. Facial photographs will be taken at every visit except Visits 3 and 9.

At selected sites, photographs of the face will be recorded using the photography equipment supplied by the photography vendor. At all other sites, photographs will be taken using on-site equipment.

7.3 Assessment of Pharmacokinetics (not applicable)

No pharmacokinetics determinations will be assessed during this study.

7.4 Assessment of Safety

7.4.1 Adverse Events

7.4.1.1 General Considerations

An adverse event (AE) is defined as any untoward medical occurrence in a subject or clinical investigation subject administered a pharmaceutical product and does not necessarily have a causal relationship with the treatment. An AE can therefore be any unfavorable and unintended sign (including an abnormal laboratory finding), symptom, or disease temporally associated with the use of a medicinal (investigational) product, whether or not considered related to the medicinal (investigational) product.

In this study, information about all AEs, whether volunteered by the subject, discovered by the investigator through questioning, or detected through physical examination, laboratory tests, or other means, will be collected and recorded on the Adverse Event page of the CRF. Abnormal laboratory values or test results will be recorded as AEs only if (1) they induce clinical signs or symptoms, (2) require therapy, or (3) are considered by the investigator to be of clinical significance. Prior medical conditions/diseases will be considered AEs only if they worsen after the start of protocol-specified study procedures. For each AE, the AE record will include start and stop dates, severity (mild, moderate, or severe), relationship to the study treatment (definite, probably, possibly, unlikely, or not related), actions taken, and outcome.

Adverse events are collected beginning after the first administration of study medication. Adverse events occurring before starting study treatment but after signing the informed consent form are to be recorded on the Medical History page of the CRF. In the PTP, information will be collected only for serious adverse events (SAE) related to study medication.

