Evaluation Criteria:	
The primary endpoint during the ATP will be the change from Baseline to the end of ATP (Week 20/Visit 8) in the acne-specific quality of life (acne-QOL) questionnaire score for those subjects who complete the 20-week ATP and are at least 75% compliant with the treatment regimen.
 
Secondary endpoints for the ATP will be:
 
 • The change from Baseline in the lesion count (nodules and inflammatory lesions) at the end of the ATP;

	
 • The change from Baseline in the acne-QOL score at Weeks 4, 8, 12, and 16 weeks; • The change from Baseline in the IGA at the end of the ATP in subjects who complete the 20-week ATP; • Treatment safety, as determined by the frequency and severity of adverse events (AEs) and local skin irritation. 
Primary endpoints for the PTP will be to determine:
 
 • The proportion of subjects who require retreatment with oral isotretinoin at any time during the PTP; and • The time at which retreatment is required. 
Secondary endpoints for the PTP will be to determine:
 
 • The proportion of subjects who require treatment with a prescription anti-acne medication other than oral isotretinoin at any time during the PTP; • The proportion of subjects who use an over-the-counter (OTC) anti-acne medication at any time during the PTP; • The severity of acne (lesion count and IGA) at the time of retreatment in subjects treated with a prescription or OTC anti-acne treatment; • The severity of acne (lesion count and IGA) at each visit; • The time to retreatment with a prescription or over-the-counter (OTC) anti-acne medication at any time during the PTP; • The acne-QOL at the end of the PTP; • Safety as assessed through the monitoring of AEs, laboratory test results, vital signs, and physical examinations.
Pharmacokinetics Evaluation Criteria:	Not applicable
Safety Evaluation Criteria:	During the ATP: adverse event (AE) incidence and severity, laboratory test results (hematology, serum biochemistry, lipid profile), pregnancy tests, vital signs (systolic and diastolic blood pressure, heart rate, respiratory rate) During the PTP: Serious AEs related to study drug.

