- e. Females of childbearing potential must have a second, confirmatory pregnancy test with negative results that occurs after the 30-day waiting period.
- f. Specified sites will perform photography using equipment supplied by the photography vendor; other sites will use on-site photography equipment.
- g. Only nodules will be counted at Screening.

Table 1-2 Visit Schedule and Assessments – Post-Treatment Phase (PTP)

	Visit 9	Visit 10	Visit 11	Visit 12	Visit 13	Visit 14/EOS
	Week 24 ± 4 days	Week 32 ± 2 weeks	Week 46 ± 2 weeks	Week 72 ± 2 weeks	Week 98 ± 2 weeks	Week 124 ± 2 weeks
Vital signs and weight	X					
Clinical laboratory assessment ^a	X					
Serum chemistry						
Pregnancy test	X					
Prior and concomitant medication assessment	X	X	X	X	X	X
Photography ^b		X	X	X	X	X
Quality of Life Questionnaire		X	X	X	X	X
Investigator's Global Assessment (IGA)		X	X	X	X	X
Lesion count (nodules and inflammatory lesions)		X	X	X	X	X
Adverse event assessment ^c	X	X	X	X	X	X

a. Laboratory assessments at Visit 9 will include fasting clinical chemistry and fasting lipid profile.

b. Specified sites will perform photography using equipment supplied by the photography vendor; other sites will use on-site photography equipment.

c. Only serious adverse events related to study treatment will be collected.

TABLE OF CONTENTS

1.0	SYNOPSIS	2
TABLE OF CONTENTS		7
LIST OF TABLES		11
LIST OF FIGURES		11
LIST OF ABBREVIATIONS AND DEFINITION OF TERMS		12
2.0	INTRODUCTION	14
2.1	Background	14
2.2	Rationale of the Study	15
2.3	Benefit-Risk Assessment	15
3.0	TRIAL OBJECTIVES AND PURPOSE	16
3.1	20-Week Active Treatment Period (ATP)	16
3.2	104-Week Post-Treatment Period (PTP)	17
4.0	STUDY DESIGN	17
4.1	Overall Study Design	17
4.2	Study Endpoints	18
4.2.1	Active Treatment Period	18
4.2.1.1	Primary Endpoint for the ATP	18
4.2.1.2	Secondary Endpoints for the ATP	19
4.2.2	Post-Treatment Period	19
4.2.2.1	Primary Endpoints for the PTP	19
4.2.2.2	Secondary Endpoints for the PTP	19
5.0	SELECTION OF STUDY POPULATION	20
5.1	Subject Population	20
5.2	Inclusion Criteria	20
5.2.1	General Inclusion Criteria	20
5.2.2	Specific Inclusion Criteria	20
5.3	Exclusion Criteria	21
5.3.1	General Exclusion Criteria	21
5.3.2	Female Specific Exclusion Criteria	21
5.3.3	Concurrent Disease Exclusion Criteria	22
5.3.4	Hypersensitivity/Allergy Exclusion Criteria	22
5.3.5	Prohibited Medication Before and/or During the Study	22

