7.4.1.3 Relationship of an Adverse Event to Study Treatment

An adverse reaction (AR) is any AE caused by a drug. A suspected adverse reaction (SAR) means any AE for which there is a reasonable possibility that the drug caused the AE, ie, there is evidence to suggest a causal relationship between the drug and the AE. Thus, an AR is a SAR for which there is reason to conclude that the drug caused the event.

The determination of the causal relationship between the drug and the AE will be based in part on the investigator's assessment of the relationship of the AE to the investigational treatment. An AE considered by the investigator to be probably or definitely related to the study treatment is to be considered an AR, and an AE considered by the investigator to be possibly related to the study treatment is an SAR, but not an AR. An AE considered by the investigator unlikely to be related, or to be unrelated, to the study treatment, is not an SAR, unless the sponsor determines otherwise based on other evidence.

The relationship between an AE and the study medication is determined by the Investigator on the basis of his or her clinical judgment and the definitions outlined in [Table 7-3](#).

Table 7-3 Terms for Defining Relationship of Adverse Event to Study Product

Association	Definition
Not related	There is no temporal relationship to trial medication administration (too early, too late or trial medication not administered), or there is a reasonable causal relationship between another treatment, concurrent disease or circumstance and the AE.
Unlikely related	A clinical event, including laboratory test abnormality (if applicable), with an improbable time sequence to product administration and in which other drugs, chemicals for underlying disease provide plausible explanations.
Possibly related	There is a reasonable causal relationship between the trial medication and the AE. The reaction follows a reasonable temporal sequence from drug administration. Dechallenge information is lacking or unclear.
Probably related	There is a reasonable causal relationship between the study medication and the AE. The reaction follows a reasonable temporal sequence from drug administration and cannot be reasonably explained by the known characteristics of the subject's clinical state, by toxic or environmental agents, or by concomitant medications. The event responds to dechallenge. Rechallenge is not required.

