7.4.1.4 Serious Adverse Event

An AE or SAR is considered “serious” if, in the view of either the investigator or sponsor, it results in any of the following outcomes:

- death;
- is life-threatening;
- inpatient hospitalization or a prolongation of an existing hospitalization;
- a persistent or significant disability/incapacity;
- a congenital anomaly/birth defect.

Important medical events that may not result in death, be life-threatening, or require hospitalization may be considered serious when, based upon appropriate medical judgment, they may jeopardize the subject or patient and may require medical or surgical intervention to prevent one of the outcomes listed in this definition. An AE or SAR is considered “life-threatening” if, in the view of either the investigator or the sponsor, its occurrence places the subject or patient at immediate risk of death. It does not include an AE or SAR that, had it occurred in a more severe

form, might have caused death. As with the definition of “serious,” the determination of whether an AE is life-threatening can be based on the opinion of either the investigator or sponsor. Thus, if either believes that an AE meets the definition of life-threatening, it must be considered life-threatening, and therefore serious, for reporting purposes. An AE can be severe without being serious.

Serious adverse events (SAEs) which occur during clinical trials are subject to legal reporting requirements. Therefore, in this study, the occurrence of any SAE from the time of informed consent until 4 weeks after the last subject visit will be reported to the Sponsor within 24 hours of its having come to the attention of the Investigator. The SAE will be recorded using the designated Serious Adverse Event Report form, which includes all legally required data (and must include an assessment of whether there is a reasonable possibility that the drug caused the event). The SAE will also be reported to the responsible Institutional Review Board (IRB) according to that IRB’s reporting requirements. Study endpoints that are SAEs (eg, mortality) are to be reported in accordance with the protocol unless there is evidence suggesting a causal relationship between the drug and the event (eg, death from anaphylaxis); in that case, the Investigator must immediately report the event to the Sponsor.

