7.4.2 Serious Adverse Event Reporting by Investigator

Any SAE, whether or not deemed drug related or expected, must be reported immediately to the sponsor as soon as it becomes known to the investigator and not later than within 24 hours of his/her knowledge of the occurrence of an SAE. The investigator will document such events in the best possible detail on the SAE Report Form to be transmitted to the sponsor.

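### The protocol gives two incompatible rules for collecting SAEs during the 104-week post-treatment period, and does not say which one governs

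*Combined protocol and SAP*

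**What the plan says.** Four places limit collection after treatment to SAEs judged related to study drug:

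- Section 7.4.1.1: "In the PTP, information will be collected only for serious adverse events (SAE) related to study medication".
- Synopsis, safety evaluation criteria: "During the PTP: Serious AEs related to study drug".
- Table 1-2, footnote c, attached to the adverse event row for Visits 9 to 14: "Only serious adverse events related to study treatment will be collected".
- Section 7.2.7, procedures for Visits 10 to 14: "Record any SAEs related to study medication".

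Three places require every SAE:

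- Section 7.4.1.4, which also sets a 24-hour deadline: "the occurrence of any SAE from the time of informed consent until 4 weeks after the last subject visit will be reported".
- Section 7.4.2: "Any SAE, whether or not deemed drug related or expected, must be reported immediately to the sponsor".
- Section 13.2.2: an SAE report form, with an assessment of relationship, for each SAE.

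Visit 9 (Week 24) also lies in the PTP. Its procedures in Section 7.2.6 say "Record any AEs", which agrees with neither footnote c nor an SAE-only rule.

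Section 3.2 makes long-term safety over the 2-year PTP a secondary objective. The matching endpoint in Section 4.2.2.2 lists AEs, laboratory results, vital signs and physical examinations. Section 8.5 provides listings and frequency summaries, does not say which set of SAEs is summarised for the PTP, and leaves the detail to the SAP.

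**The concern.** An investigator who learns of an SAE a year after a subject's last capsule, and who thinks it unrelated, cannot satisfy both sets of instructions. One set says that it is not collected. The other says that it goes to the sponsor within 24 hours.

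Two things are at stake. The first is the meaning of the PTP safety result. Sites that follow different sections would feed different kinds of SAE data into one pooled summary. Where the related-only rule is followed, a low count says as much about the filter as about the drug. The second is oversight. Section 7.4.1.3 lets the sponsor override a site's judgment that an event is unlikely to be related or is unrelated, but the sponsor cannot review an event that the site did not send.

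**Working it through.** The documents give no SAE rate or expected event count, so there is no stated figure to reproduce. The check is mainly textual.

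**1. Do the rules overlap in time?** Section 4.1 gives a 20-week treatment period, a 104-week PTP and 124 weeks in total: 20 + 104 = 124, which agrees. The window in Section 7.4.1.4 opens at consent and closes 4 weeks after the last subject visit, so it contains the whole PTP. Section 7.4.2 has no end date. The overlap is 104/124 = 83.9% of the study.

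**2. Do they differ in content?**

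| SAE in the PTP, as judged by the site | 7.4.1.1, 7.2.7, footnote c, synopsis | 7.4.1.4, 7.4.2, 13.2.2 |
|---|---|---|
| Possibly, probably or definitely related | Collected | Reported |
| Unlikely or not related | Not collected | Reported |

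The second row is the conflict. The table takes related to mean possibly related or higher, in line with the definition of a suspected adverse reaction in Section 7.4.1.3. The collection passages do not themselves say which categories count.

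**3. How does the causality scale treat late events?** Table 7-3 gives as one ground for *Not related*: "There is no temporal relationship to trial medication administration (too early, too late or trial medication not administered". No time window defines too late. *Probably* needs a response to dechallenge and *Definitely* a response to withdrawal. Neither can be observed for an event that starts after dosing has ended, so *Possibly* is in practice the highest category open to it. *Possibly* needs a reasonable temporal sequence and accepts missing dechallenge information.

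**4. What other safety data does the PTP yield?** Table 1-2 schedules vital signs and laboratory tests at Visit 9 only, and no physical examination at any PTP visit. From Week 24 to Week 124 there are 100 weeks, or 100/104 = 96.2% of the PTP, with none of these scheduled.

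**5. How much could the choice of rule matter?** This is an illustration only. Take n = 140, the approximate number expected to complete treatment (Section 5.1). Let π be the 2-year SAE risk and q the share of late SAEs judged related. The documents give neither, so both are assumptions.

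- Expected SAEs recorded: nπ under the all-SAE rule, nπq under the related-only rule.
- Chance of recording none: (1 − π)^n and (1 − πq)^n.
- With π = 2%, all-SAE rule: 140 × 0.02 = 2.8 expected; 0.98^140 = 5.9% chance of none.
- With π = 2% and q = 10%, related-only rule: 140 × 0.02 × 0.10 = 0.28 expected; 0.998^140 = 75.6% chance of none.
- Over π = 1% to 5%, the chance of none runs from 24.5% down to 0.1% under the all-SAE rule, and from 86.9% down to 49.6% under the related-only rule with q = 10%.
- At π = 2%, the related-only chance of none is 86.9% for q = 5%, 49.6% for q = 25%, 24.5% for q = 50% and 5.9% for q = 100%.

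If no event is recorded, the upper limit of the two-sided 95% interval is 1 − 0.025^(1/140) = 2.6%. Under the related-only rule that limit applies to SAEs judged related, not to all SAEs.

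**The case against.** The best defence is that there are two channels. Section 7.4.1.1 speaks of the adverse event page of the CRF, while Section 7.4.1.4 speaks of a separate SAE report form. Their start points already differ: AEs are collected after the first dose, SAEs are reported from consent. On that reading every SAE reaches the sponsor, with causality recorded, and only the CRF is restricted. This is plausible, and it means that loss of SAE data is not established. But the protocol never says it. The Section 7.4.1.1 sentence limits what information is collected at all, and Section 8.5 would still not say which set is summarised.

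A reader might infer from Table 7-3 that a late SAE must be called unrelated. The table does not support that. Too late has no cut-off, *Unlikely* needs a plausible alternative explanation as well as an improbable time sequence, *Possibly* stays open, and the call also rests on clinical judgment.

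A reader might also put a number on the loss by taking 140 × 2 = 280 subject-years and an SAE rate. The documents give no such rate. The 280 is also an upper bound, because Section 4.1 withdraws subjects who are prescribed isotretinoin again, and Section 2.1 cites relapse in about 23% of patients, mainly in the first two years.

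The effect on expedited review is limited too. SAEs that the site judges possibly related or higher are captured under either rule, so the difference is confined to those judged unlikely or unrelated.

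**Conclusion.** The passages contradict each other for the whole PTP, 104 of 124 weeks, and must be reconciled. That conclusion rests on the text alone.

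The consequence for the safety objective is conditional. If sites follow the related-only passages, SAEs that they judge unlikely or unrelated are not collected, the sponsor cannot revisit those judgments, and a low PTP count could reflect the collection rule. This carries weight because, for the last 100 weeks, the schedule offers none of the other safety measurements named in the endpoint.

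It is tempting to say that the long-term safety question is answered almost by construction. The documents do not support this. It would need both that the related-only rule governs and that few late SAEs are judged related. Neither is stated, and the illustration swings from 5.9% to 86.9% on the second condition alone. How many SAEs would be lost cannot be derived from the documents. No sample size or power figure is affected, since Section 8.2 plans no hypothesis tests.

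**What to change.** Adopt the rule that Sections 7.4.1.4 and 7.4.2 already contain, and align the other passages with it:

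- Reword the synopsis line, Table 1-2 footnote c, the Section 7.2.7 bullet and the Section 7.4.1.1 sentence so that all SAEs are collected through the PTP.
- Record the site's causality judgment as a data field for each SAE, as Section 13.2.2 already asks, and do not use it to decide what is collected.
- State in Section 8.5 and the SAP that PTP SAEs are tabulated both all-cause and related, and give the denominator.
- While footnote c is being edited, reconcile it with the Visit 9 instruction in Section 7.2.6.

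The cost is a protocol wording amendment and a few more SAE forms over two years, with no new visits or procedures. The change does not supply the laboratory, vital sign and examination data that Section 4.2.2.2 also names for the PTP; it settles only what the SAE count means.
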